7.1.1. Use of Electronic Diaries

At the time of consent, the participants must confirm they will be willing to complete an eDiary using either an application downloaded to their smartphone or using a device that will be provided at the time of enrollment. Before enrollment on Day 1, the participant will be instructed to download the eDiary application or will be provided an eDiary device to record solicited ARs ([Section 7.4.3](#)) on Day 1.

On Day 1 (dosing day), participants will be instructed on thermometer usage to measure body temperature, ruler usage to measure injection site erythema and swelling/induration (hardness), and self-assessment for localized axillary swelling or tenderness on the same side as the injection arm.

On Day 1 (dosing day), participants will record data into the eDiary starting approximately 30 minutes after the injection under supervision of the study site staff to ensure successful entry of assessments. The study site staff will perform any retraining as necessary. Participants will continue to record data in the eDiary after they leave the study site, preferably in the evening and at the same time each day, on the day of injection and for 6 days following injection.

Participants will record the following data in the eDiary:

- Solicited local and systemic reactogenicity ARs, as defined in [Section 7.4.3](#), that occur on the day of vaccination and during the 7 days after vaccination (ie, the day of injection and 6 subsequent days). Any solicited AR that is ongoing beyond Day 7 will be reported in the eDiary until it has resolved, and not to exceed 28 days after vaccination. ARs recorded in the eDiary beyond Day 7 should be reviewed by the

study site staff either during the next scheduled telephone call or at the next study site visit.

- Daily oral body temperature measurement should be performed at approximately the same time each day using the thermometer provided by the study site. If body temperature is taken more than once in a given day, only the highest temperature reading should be recorded.
- Other measurements, as applicable, for solicited local ARs (injection site erythema and swelling/induration) will be performed using the ruler provided by the study site.
- Any medications taken to treat or prevent pain or fever on Day 1 or for the next 6 days.

The eDiary will be the only source document allowed for solicited systemic or local ARs (including body temperature measurements). Participants will be instructed to complete eDiary entries daily. The participant will have a limited window on the following day to complete assessments for the previous day; quantitative temperature recordings and measurement of any injection site erythema or swelling/induration reported on the following day may be excluded from the analyses of solicited ARs.

Any new safety information reported during safety telephone calls or at site visits (including a solicited AR) that is not already captured in the eDiary will be described in the source documents as a verbally reported event. Any AR reported in this manner must be described as an unsolicited event and therefore entered on the AE eCRF.

Study site staff will review eDiary data with participants during the safety call 7 days after vaccination.

The eDiary will also be used every 2 weeks from Day 36 to Day 162, and from Day 202 to Day 342 (Parts A.1, B, C, D, F, and G only) or every 2 weeks from Day 36 to Day 162 (Parts A.2, H, and J only), to capture the occurrence of MAAEs, AESI, SAEs, and AEs leading to withdrawal. The eDiary will prompt the participant to complete an eDiary questionnaire that collects the following data:

- Changes in health since last completing the questionnaire or since in contact with the study site.
- Known exposure to someone with known COVID-19 or SARS-CoV-2 infection.
- Any experience of symptoms of COVID-19.
- Any MAAEs, AESI, or SAEs.

If an eDiary record results in identification of relevant safety events or of symptoms of COVID-19, a follow-up safety call will be triggered.

Apart from the safety telephone calls described in [Section 7.1.2](#), each participant will complete a questionnaire in an eDiary as shown in the SoE ([Table 17](#), [Table 18](#), [Table 19](#), and [Table 20](#)). The eDiary responses will be reviewed by study site personnel and may result in a follow-up safety call by the site to the participant.

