7.4. Safety Definitions and Related Procedures

7.4.1. Adverse Event

An AE is defined as any untoward medical occurrence associated with the use of a drug in humans, whether or not considered drug related.

Events Meeting the Adverse Event Definition

- Exacerbation of a chronic or intermittent pre-existing condition including either an increase in frequency and/or intensity of the condition.
- New conditions detected or diagnosed after vaccination even though they may have been present before the start of the study.

Events NOT Meeting the Adverse Event Definition

- Procedures planned before study entry (eg, hospitalization for preplanned surgical procedure).
- Medical or surgical procedure (eg, endoscopy, appendectomy): the condition that leads to the procedure should be the AE.
- Situations in which an untoward medical occurrence did not occur (social and/or convenience admission to a hospital).

An AR is any AE for which there is a reasonable possibility that the vaccine caused the AE ([Section 7.4.3](#)). For the purposes of investigational new drug safety reporting, “reasonable possibility” means that there is evidence to suggest a causal relationship between the vaccine and the AE.

An unsolicited AE is any AE reported by the participant that is not specified as a solicited AR in the protocol or is specified as a solicited AR but starts outside the protocol-defined period for reporting solicited ARs (ie, 7 days after vaccination). Any unsolicited AE which began during mRNA-1273-P301 (COVE) but is ongoing at the time of enrollment in this study, should be documented as medical history.

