6.3.2. Solicited Adverse Reactions

6.3.2.1. Analysis of Solicited Adverse Reactions

The solicited ARs are recorded by the subject in eDiary. If a solicited local or systemic AR continues beyond 7 days post injection, the participant will be prompted to capture solicited local or systemic AR in the eDiary until resolution.

Analyses of solicited ARs will be provided based on the Solicited Safety Set. The following summaries will be provided.

- Summary of SAR Within 7 Days (SAR eDiary and SAR eCRF)
 - i. The number and percentage of subjects who reported each individual solicited local AR and solicited systemic AR during the 7-day follow-up period after the injection will be tabulated by severity grade.
A two-sided 95% exact confidence interval (CI) using the Clopper-Pearson method will be provided for the percentage of subjects who reported any solicited local AR, solicited systemic AR, or any solicited AR.
 - ii. The number and percentage of subjects who reported each individual solicited local AR and solicited systemic AR during the 7-day follow-up period after the injection will be summarized by onset day (Day 1 through Day 7). The onset of

individual solicited AR is defined as the time point after the injection at which the respective solicited AR first occurred.

- Summary of SAR Duration (SAR eDiary and SAR eCRF)
 - i. Duration is calculated as the last day – the first day + 1 when the solicited adverse reaction was reported starting within the 7 days of injection.
- Summary of SAR Persisting Beyond 7 Days (SAR eDiary and SAR eCRF)
 - i. The number and percentage of subjects who reported each individual solicited local AR and solicited systemic AR that persist beyond 7 days after the injection (i.e., occurred before day 7, but persisting after day 7 regardless of duration) will be tabulated by severity grade.

A two-sided 95% exact confidence interval (CI) using the Clopper-Pearson method will be provided for the percentage of subjects who reported any solicited local AR, solicited systemic AR, or any solicited AR persisting beyond 7 days after injection.
- Summary of SAR with Onset after Day 7 (SAR eCRF only)
 - i. The incidence for each individual solicited local AR and solicited systemic AR with onset day after the 7-day follow-up period after the injection (i.e., after Day 7) will be tabulated.

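### The recording and tabulation rules for solicited reactions do not fit together, so reactions that persist from Day 7, start after Day 7 or are reported verbally can be misclassified or under-counted.

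*Protocol*

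**What the plan says.** Protocol 7.4.1 and the glossary classify by onset. An event on the solicited list becomes unsolicited when it "is specified as a solicited AR but starts outside the protocol-defined period for reporting solicited ARs", that period being 7 days after vaccination. Protocol 7.4.4 and 7.4.10 record unsolicited AEs on the AE page of the eCRF.

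Protocol 7.1.1 classifies by reporting route. It states: "The eDiary will be the only source document allowed for solicited systemic or local ARs (including body temperature measurements"). New safety information from calls or visits ("including a solicited AR) that is not already captured in the eDiary will be described in the source documents as a verbally reported event") follows a different path: "Any AR reported in this manner must be described as an unsolicited event and therefore entered on the AE eCRF". No onset limit is attached.

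Protocol 7.4.3 requires a separate solicited-reaction eCRF page for a solicited reaction that leads to a healthcare visit, leads to withdrawal, lasts beyond 7 days, or is serious. Onset after Day 7 is not on that list.

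SAP 6.3.2.1 names its sources table by table (SAR is its abbreviation for solicited adverse reaction):
- The 7-day summary is "Summary of SAR Within 7 Days (SAR eDiary and SAR eCRF"), with onset tabulated from Day 1 to Day 7.
- The persisting summary is explained as reactions that "occurred before day 7, but persisting after day 7 regardless of duration".
- The late-onset summary is "Summary of SAR with Onset after Day 7 (SAR eCRF only").

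**The concern.** Solicited local and systemic reactions over 7 days are a primary safety endpoint in every part (SAP 3.1). When one rule sorts by onset and another by reporting route, the same reaction on the same day can be solicited for one participant and unsolicited for another. Rates then depend partly on eDiary completion, which may differ by site and part.

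Rerouting also changes how the event is assessed. A solicited reaction is graded on the Table 14 scale and is always taken as related (Protocol 7.4.3). An unsolicited event is graded mild, moderate or severe, with causality judged by the investigator (Protocol 7.4.8 and 7.4.9).

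The persisting and late-onset tables describe delayed reactogenicity. Protocol 1.4.2 reports injection-site reactions after Day 7 in the pivotal trial, so these tables should be complete.

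**Working it through.** The plan states no figure to reproduce. The check follows each onset day and reporting route through the recording rules and then the SAP tables. The solicited window is the injection day plus 6 days (Protocol 7.1), which is Day 1 to Day 7 under the SAP 6.1 study-day formula.

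| Onset and route | 7-day table | Persisting table | Onset-after-Day-7 table |
|---|---|---|---|
| Day 1–6, eDiary, over by Day 7 | yes | no | no |
| Day 1–6, eDiary, continues | yes | yes | no |
| Day 7, eDiary, continues | yes | **no** | **no** |
| Day 8 or later, AE page | no | no | **only if also on the solicited-reaction page** |
| Day 1–7, verbal only, no 7.4.3 trigger | **no** | no | no |
| Day 1–7, verbal only, 7.4.3 trigger met | **depends on which section the site followed** | depends | no |

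(a) Day 7 onset. Before Day 7 means Days 1 to 6, and after Day 7 means Day 8 onward. A reaction running from Day 7 to Day 12 meets neither condition. It is still counted in the 7-day, onset-day and duration summaries.

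(b) Late onset. The onset-based definition makes the event unsolicited, and 7.4.4 and 7.4.10 put it on the AE page. The SAP table reads only the other page.

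(c) Verbal reports. 7.1.1 puts a Day 3 reaction mentioned only at the Day 8 call on the AE page, although it does not meet the 7.4.1 definition of unsolicited. It then appears in the unsolicited treatment-emergent AE tables (SAP 6.3.1) and in no solicited table, unless a 7.4.3 trigger also took it to the solicited-reaction page.

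Illustration of how (c) scales, on assumptions not in the documents. If m is the share of participants with a given reaction who reported it only verbally, and the denominator is unchanged, observed rate = true rate × (1 − m). With an assumed true rate of 65%:
- m = 1%: 0.65 × 0.99 = 64.4%
- m = 5%: 0.65 × 0.95 = 61.8%
- m = 10%: 0.65 × 0.90 = 58.5%

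This concerns a single reaction. For any solicited reaction the loss is smaller, because a participant leaves the numerator only if no other reaction is in the eDiary. A participant with no solicited data at all also leaves the Solicited Safety Set (SAP 5.6), so the direction is then not fixed.

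**The case against.** Restricting solicited rates to the eDiary is a defensible, prespecified choice. Severity is graded automatically from participant entries, and recalled verbal reports are of a different quality. There are safeguards: a supervised first entry about 30 minutes after injection, a limited next-day entry window, and an eDiary review with every participant at the Day 8 call. This stands, and it is why the main 7-day table should keep its sources. It does not remove the conflict between 7.1.1, 7.4.1 and 7.4.3.

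The 7.4.3 list says when the solicited-reaction page must be used, not that nothing else may go there. The eCRF release on which the SAP is based is not available here, and the SAP's late-onset table presupposes that the page can hold such events. This also stands. The table can be incomplete, but the documents do not show that it will be nearly empty.

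The main text of the persisting rule speaks of reactions continuing beyond 7 days, and only the explanatory gloss excludes Day 7 onset. The gloss is nevertheless the operational definition that a programmer would follow.

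A reader might infer that the SAP misses Day 7 onset altogether. It does not: the gap is confined to the persisting table. Nor are verbally reported events lost, since they reach the unsolicited tables.

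**Conclusion.** The three inconsistencies are real and can be read directly from the text. Applied literally, the SAP drops every continuing reaction with Day 7 onset from the persisting table. It can leave the late-onset table incomplete, and it keeps some verbally reported Day 1 to 7 reactions out of the 7-day table.

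The size is unknown, because neither document gives the share of reactions reported only verbally, the frequency of Day 7 onset, or the completion rules for the solicited-reaction page. A reader might conclude that solicited-reaction rates are too low as a matter of fact. The documents support only a risk of misclassification or under-counting. Safety analyses are descriptive (Protocol 8.5.4), so no hypothesis test or decision rule is affected.

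**What to change.** In SAP 6.3.2.1:
1. Define persisting reactions by onset on or before Day 7.
2. Build the onset-after-Day-7 table from AE-page records of the listed reaction terms as well as the solicited-reaction page, counting a participant once per reaction.
3. Keep the primary 7-day table on its current sources, and add a sensitivity summary that also counts AE-page records of listed reactions with onset on Day 1 to 7. Present it at any severity, because AE-page events are not graded on the Table 14 scale.

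Fix the mapping from preferred terms to listed reactions before database lock.

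Reconcile Protocol 7.1.1, 7.4.1 and 7.4.3 on which eCRF page takes verbally reported Day 1 to 7 reactions and late-onset reactions. By inference this will not alter collection. Amendment 11 is dated 10 October 2023, and last completion is estimated at December 2023 with at least 6 months of follow-up, so the Day 1 to 7 periods were probably over. The SAP changes are the ones that affect the results.

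The AE page already holds event type and onset time (Protocol 7.4.10), so no new data are needed. The cost is some programming and term matching, and the sensitivity rates may be slightly higher than the primary ones.

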7.1.1.1. Ancillary Supplies for Participant Use

Study sites will distribute Sponsor-provided oral thermometers and rulers for use by participants to assess body temperature and injection site reactions, respectively, for recording solicited ARs in the eDiaries. Based on availability, smartphone devices may be provided to those participants who do not have their own device to use for eDiary activities.

7.1.2. Safety Telephone Call

A safety telephone call is a telephone call made to the participant by a trained site personnel. This call will follow an approved script, which will facilitate the collection of relevant safety information. There will be a safety telephone call on Day 8 for each participant to discuss their health and review their eDiary. Subsequent safety calls by the site to each participant will occur every 2 weeks from Day 43 to Day 169, and from Day 209 to Day 349 (Parts A.1, B, C, D, F, and G only) ([Table 17](#)) and every 2 weeks from Day 43 to Day 169 for Parts A.2 ([Table 18](#)), H ([Table 19](#)), and J ([Table 20](#)). The participant will be interviewed according to the script about the occurrence of AEs, MAAEs, AESI, SAEs, AEs leading to withdrawal, concomitant medications associated with those events, and any non-study vaccinations ([Section 7.4.7](#)). In addition, study personnel will collect information on known participant exposure to someone with COVID-19 or SARS-CoV-2 infection and on the participant's experience of COVID-19 symptoms. All safety information collected from the telephone call must be documented in the source documents as described by the participant and not documented on the script used for the safety telephone contact. As noted in [Section 7.1.1](#), an unscheduled follow-up safety call may be triggered if an eDiary record results in identification of a relevant safety event.

7.1.3. Laboratory Assessments

No routine safety laboratory assessments are planned for this study.

A point-of-care urine pregnancy test will be performed at Day 1 before vaccination. At any time, a pregnancy test either via blood or point-of-care urine can be performed, at the discretion of the investigator. If not documented in a female participant's medical records, an FSH test may be performed at the Screening Visit, as necessary and at the discretion of the investigator, to confirm postmenopausal status.

7.1.4. Vital Sign Measurements

Vital sign measurements will include systolic and diastolic blood pressure, heart rate, respiratory rate, and body temperature (preferred route is oral). The participant will be seated for at least 5 minutes before all measurements are taken. Vital signs will be measured at the time points indicated in the SoE ([Table 17](#), [Table 18](#), [Table 19](#), and [Table 20](#)). Vital signs are to be collected pre- and post-dosing on the day of injection (Day 1) only. When applicable, vital sign measurements should be performed before blood collection.

Participants who are febrile (body temperature $\geq 38.0^{\circ}\text{C}$ [100.4°F]) before injection on Day 1 must be rescheduled within the relevant window period to receive the injection. Afebrile participants with minor illnesses may be vaccinated at the discretion of the investigator.

7.1.5. Physical Examinations

A full physical examination, including height and weight, will be performed at Day 1 as indicated in the SoE ([Table 17](#), [Table 18](#), [Table 19](#), and [Table 20](#)). The full examination will include assessment of skin, head, ears, eyes, nose, throat, neck, thyroid, lungs, heart, cardiovascular system, abdomen, lymph nodes, and musculoskeletal system and extremities. Any clinically significant finding identified during a study visit should be reported as an MAAE.

Symptom-directed physical examinations may be performed at other time points at the discretion of the investigator. On the day of vaccination, before injection, the arm receiving the injection should be examined and the associated lymph nodes should be evaluated.

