Lost to follow-up	A participant who repeatedly fails to return for scheduled visits without stating an intention to withdraw consent and is unable to be contacted by the study site.
Medically attended adverse event (MAAE)	An AE that leads to an unscheduled visit to a healthcare provider.
Nonchildbearing potential	Surgically sterile (history of bilateral tubal ligation, bilateral oophorectomy, hysterectomy) or postmenopausal (defined as amenorrhea for \geq 12 consecutive months prior to screening without an alternative medical cause).
Screen failures	Participants who consent to participate in the clinical study but are not subsequently assigned to treatment.
Serious adverse event (SAE)	
An AE is considered an SAE, if, in the view of either the investigator or Sponsor, it results in any of the following outcomes (see Section 7.4.2 for further details of each criterion):
 
Death
 
Is life-threatening
 
Inpatient hospitalization or prolongation of existing hospitalization
 
Persistent or significant incapacity or substantial disruption of the ability to conduct normal life functions
 
Congenital anomaly or birth defect
 
Medically important event.

Symptomatic COVID-19	The presence of one of the CDC-listed symptoms (CDC 2022) and a positive RT-PCR test on a respiratory sample.
Unsolicited AE	Any AE reported by the participant that is not specified as a solicited AR in the protocol or is specified as a solicited AR but starts outside the protocol-defined period for reporting solicited ARs (ie, 7 days after vaccination).
Women of childbearing potential	Women of childbearing potential are those who are considered fertile following menarche and until becoming postmenopausal unless permanently sterile (see Section 10.3 , Appendix 3).

Abbreviations: AE = adverse event; AESI = adverse event of special interest; AR = adverse reaction;

MAAE = medically attended adverse event; RT-PCR = reverse transcriptase polymerase chain reaction;

SAE = serious adverse event.

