2. OBJECTIVES AND ENDPOINTS

This study consists of 9 parts: A (1, 2), B, C D, E, F, G, H, and J. The objectives and endpoints in each part are described in the tables below, Part E objectives and endpoints are described in a site-specific protocol amendment and are not covered in this global protocol amendment. The objectives and endpoints for Parts A (1, 2), B, C, and D are described below in [Table 1](#), [Table 2](#), [Table 3](#), [Table 4](#), and [Table 5](#), respectively, the objectives and endpoints for Part F (Cohorts 1 and 2) are described in [Table 6](#) and [Table 7](#), the objectives and endpoints for Part G are described in [Table 8](#), the objectives and endpoints for Part H are described in [Table 9](#), and the objectives and endpoints for Part J are described in [Table 10](#).

Table 1: Part A.1 – 50 µg mRNA-1273.211 and 100 µg mRNA-1273.211

Objectives	Endpoints
Primary	

 To evaluate the safety and reactogenicity of mRNA-1273.211 	
 Solicited local and systemic reactogenicity ARs during a 7-day follow-up period after vaccination Unsolicited AEs during the 28-day follow-up period after vaccination SAEs, MAAEs, AEs leading to withdrawal and AESI from Day 1 to EoS
Exploratory	

 To evaluate the immunogenicity of mRNA-1273.211 at selected timepoints post boost To assess for symptomatic and asymptomatic SARS-CoV-2 infection 	
 Immune response of mRNA-1273.211 against ancestral SARS-CoV-2 and SARS-CoV-2 variants including B.1.351 at selected timepoints post boost by GMT, GMFR and SRR Laboratory-confirmed symptomatic or asymptomatic SARS-CoV-2 infection will be defined in participants: 
 Primary case definition per the mRNA-1273-P301 (COVE) study Secondary case definition based on the CDC criteria: the presence of one of the CDC-listed symptoms (CDC 2022) and a positive RT-PCR test on a respiratory sample Asymptomatic SARS-CoV-2 infection is defined as a positive RT-PCR test on a respiratory sample in the absence of symptoms or a positive serologic test for anti-nucleocapsid antibody after a negative test at time of enrollment

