7.4.4. Medically Attended Adverse Events

An MAAE is an AE that leads to an unscheduled visit to an HCP. This would include visits to a study site for unscheduled assessments (eg, abnormal laboratory follow-up, COVID-19 [[Section 7.1.6](#)]) and visits to HCPs external to the study site (eg, urgent care, primary care physician). Investigators will review unsolicited AEs for the occurrence of any MAAEs. Unsolicited AEs will be captured on the AE page of the eCRF.

All confirmed COVID-19 cases will be recorded as MAAEs.

All suspected cases of anaphylaxis should be recorded as MAAEs and reported as an SAE, based on the criteria for a medically important event, unless the event meets other serious criteria. As an SAE, the event should be reported to the Sponsor or designee immediately and in all circumstances within 24 hours per [Section 7.4.11](#). The investigator will submit any updated anaphylaxis case data to the Sponsor within 24 hours of it being available. For reporting

purposes, a participant who displays signs or symptoms consistent with anaphylaxis (as follows) should be reported as a potential case of anaphylaxis. This is provided as general guidance for investigators and is based on the Brighton Collaboration case definition ([Rüggeberg et al 2007](#)).

Anaphylaxis is an acute hypersensitivity reaction with multi-organ system involvement that can present as, or rapidly progress to, a severe life-threatening reaction. It may occur following exposure to allergens from a variety of sources.

Anaphylaxis is a clinical syndrome characterized by the following:

- Sudden onset AND
- Rapid progression of signs and symptoms AND
- Involves 2 or more organ systems, as follows:
 - **Skin/mucosal:** urticaria (hives), generalized erythema, angioedema, generalized pruritus with skin rash, generalized prickle sensation, and red and itchy eyes.
 - **Cardiovascular:** measured hypotension, clinical diagnosis of uncompensated shock, loss of consciousness or decreased level of consciousness, and evidence of reduced peripheral circulation.
 - **Respiratory:** bilateral wheeze (bronchospasm), difficulty breathing, stridor, upper airway swelling (lip, tongue, throat, uvula, or larynx), respiratory distress, persistent dry cough, hoarse voice, sensation of throat closure, sneezing, and rhinorrhea.
 - **Gastrointestinal:** diarrhea, abdominal pain, nausea, and vomiting.

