7.4.12. Time Period and Frequency for Collecting AE, AESI, and SAE Information

Medical occurrences that begin before IP dosing but after obtaining informed consent will be recorded in the Medical History/Current Medical Conditions section of the eCRF and not in the AE section; however, if the condition worsens at any time during the study, it will be recorded and reported as an AE.

AEs may be collected as follows:

- Observing the participant.
- Receiving an unsolicited complaint from the participant.
- Questioning the participant in an unbiased and nonleading manner.

Solicited AEs will be collected from the day of injection through 6 days after vaccination. Other (unsolicited) AEs will be collected from the day of injection through 28 days after vaccination.

Serious AEs (including AESI) will be collected from the start of IP dosing until the last day of study participation.

All SAEs and AESI will be recorded and reported to the Sponsor or designee immediately and under no circumstance should this exceed 24 hours of becoming aware of the event via the EDC system. If a site receives a report of a new SAE or AESI from a study participant or receives updated data on a previously reported SAE or AESI and the eCRF has been taken offline, then the site can report this information on a paper SAE or AESI form using the SAE Mailbox or the SAE Fax line ([Section 7.4.11](#)).

An abnormal value or result from a clinical or laboratory evaluation can also indicate an AE if it is determined by the investigator to be clinically significant (eg, leads to study drug discontinuation, or meets any serious criteria). If this is the case, it must be recorded in the source document and as an AE on the appropriate AE form(s). The evaluation that produced the

value or result should be repeated until that value or result returns to normal or is stabilized and the participant's safety is not at risk.

Investigators are not obligated to actively seek AEs or SAEs after EoS participation. However, if the investigator learns of any SAE (including a death) at any time after a participant has withdrawn from or completed the study, and the investigator considers the event to be reasonably related to the IP or study participation, the investigator must promptly notify the Sponsor.

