6.3.1. Adverse Events

A treatment-emergent AE (TEAE) is defined as any event occurring during the study not before exposure to study vaccine or any event already present that worsens after exposure to study vaccine. [Note: worsening of a pre-existing condition after vaccination will be reported as a new AE.]

Adverse events will also be evaluated by the investigator for the coexistence of MAAE which is defined as an AE that leads to an unscheduled visit to a healthcare practitioner.

Overview of unsolicited AEs will be summarized by stage, up to 28 days after vaccination and throughout the study (see [Section 6.1](#)).

All summary tables (except for the overall summary of AEs) for unsolicited AEs will be presented by SOC and PT for TEAEs with counts of subjects included. SOC will be displayed in internationally agreed order. PT will be displayed in alphabetical order for first booster, in descending order of frequency based on the mRNA-1273 50 µg group then alphabetically for second booster, and in descending order of frequency based on the mRNA-1273.231 50 µg group then alphabetically for third booster. When summarizing the number and percentage of subjects with an event, subjects with multiple occurrences of the same AE or a continuing AE will be counted once. Subjects will be presented according to

the highest severity in the summaries by severity, if subjects reported multiple events under the same SOC and/or PT.

Percentages will be based upon the number of subjects in the Safety Set.

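### Protocol 7.1.5 lets a new finding at a scheduled post-dose visit be reported as an MAAE, although protocol and SAP define an MAAE by an unscheduled healthcare visit

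*Protocol*

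**What the plan says.** Protocol 7.1.5 (Physical Examinations) states: "Any clinically significant finding identified during a study visit should be reported as an MAAE". The same sentence stands in footnote 3 of all four schedules of events (Tables 17 to 20). It requires neither that the finding be an AE nor that the participant sought care because of it.

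The definitions elsewhere are narrower, and they agree with one another:

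- Protocol 7.4.4: "An MAAE is an AE that leads to an unscheduled visit to an HCP". On visits to the study site it adds: "This would include visits to a study site for unscheduled assessments".
- Protocol glossary: "An AE that leads to an unscheduled visit to a healthcare provider".
- SAP 6.3.1: "MAAE which is defined as an AE that leads to an unscheduled visit to a healthcare practitioner".

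MAAEs are part of the primary safety endpoint. Protocol Section 2 lists "SAEs, MAAEs, AEs leading to withdrawal and AESI from Day 1 to EoS", and SAP 3.1 applies that endpoint to every part. SAP 6.3.1.1 and 6.3.1.2 tabulate unsolicited medically-attended treatment-emergent AEs (TEAEs), overall and by system organ class and preferred term.

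On COVID-19, protocol 7.4.4 says "All confirmed COVID-19 cases will be recorded as MAAEs", whereas protocol 7.1.6 and 3.1 assign MAAE status to confirmed symptomatic infection.

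**The concern.** One component of a primary safety endpoint has two case definitions that do not coincide. A site that follows 7.1.5 reports an MAAE for a new finding at a routine visit. A site that follows 7.4.4 records the same finding as an AE only. The label is set at the site, and the SAP describes no step that checks it against an unscheduled visit. The tabulated count can therefore depend on which section a site applied, and it can include events that involved no medical attendance beyond the planned visit.

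At stake is the meaning of a descriptive safety row and its comparability between sites and arms. No significance level, power or success criterion depends on it.

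**Working it through.** The documents give no expected MAAE rate and no rate of clinically significant findings, so there is no stated figure to reproduce. The check sets the rules side by side.

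**1. Where the two rules diverge.** They agree when a finding prompts an unscheduled visit. They diverge when a finding is first seen at a scheduled visit and leads to none. Apart from screening and Day 1, physical examination is scheduled as follows:

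- Table 17 (Parts A.1, B, C, D, F, G): Day 29, Day 91 (Parts F and G only), Day 181 and Day 366.
- Tables 18 to 20 (Parts A.2, H, J): Day 29, Day 91 and Day 181.

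**2. One case followed through.** Take a new, non-serious, clinically significant finding at the Day 181 visit that leads to no unscheduled healthcare visit.

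- Under 7.1.5 and footnote 3 it is an MAAE (count 1).
- Under 7.4.4, the glossary and SAP 6.3.1 it is not (count 0).
- Its onset is after vaccination, so it meets the TEAE definition in SAP 6.3.1, and the TEAE filter does not remove it.
- SAP 6.3.1 leaves MAAE status to the investigator's evaluation. Neither SAP 6.3.1.1 nor 6.3.1.2 derives or verifies it.

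A site following 7.1.5 therefore adds one participant to the medically-attended row, unless that participant already has another MAAE.

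**3. Other routes for the same finding.** Protocol 7.4.7 sends examination findings classified as AEs to the AE page, and 7.4.12 treats a clinically significant abnormal result as an AE. Neither attaches an automatic MAAE label, so 7.1.5 and the footnotes stand alone.

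**4. What the 7.1.5 rule may be protecting.** Under protocol 7.1, unsolicited AEs are collected for 28 days. After that only SAEs, MAAEs, AESI and AEs leading to withdrawal are collected to end of study. At Day 91, 181 and 366 the MAAE label is thus the main route by which a non-serious finding is captured. Deleting the sentence without a replacement could lose such findings.

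**5. Size, as illustration only.** Assume, without support in the documents, that a proportion p of participants has a new post-dose finding at a scheduled visit and no other MAAE. Added participants = p × arm size.

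| Arm size | p = 0.5% | p = 5% |
|---|---|---|
| 584 | 0.005 × 584 = 2.9 | 0.05 × 584 = 29.2 |
| 375 | 0.005 × 375 = 1.9 | 0.05 × 375 = 18.8 |
| 50 | 0.005 × 50 = 0.25 | 0.05 × 50 = 2.5 |

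If no such findings occur, or if every site applied 7.4.4, the excess is zero.

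**The case against.** The strongest reply is that the analysis document already has the right definition. SAP 6.3.1 ties the MAAE to an unscheduled visit, and the SAP introduction says the SAP prevails where its methods differ from the protocol's. Examinations after Day 1 are only symptom-directed and at the investigator's discretion, so such findings should be few. The summaries are descriptive, and MAAEs are shown by preferred term, so a reader can see what the count contains. All of this limits the consequence. It does not remove the conflict: a definition in the SAP cannot correct a flag that was set at the site under another rule and is not checked afterwards.

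A reader might also infer that the Day 1 full examination is the main source of false MAAEs, because 7.1.5 covers it. The documents do not support that:

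- Protocol 7.1 collects MAAEs from vaccination onward.
- Protocol 7.4.12 says: "Medical occurrences that begin before IP dosing but after obtaining informed consent will be recorded in the Medical History/Current Medical Conditions section of the eCRF".
- Protocol 7.4.10 excludes conditions present at screening that do not deteriorate.
- Protocol 7.4.7 analyses pre-dose AEs separately.
- SAP 6.3.1 counts only events that are not before exposure, or that worsen after it.

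Nor does the imputation rule in SAP Appendix D reopen that route. It acts on AE records with partial or missing start dates, and a pre-existing condition handled as instructed is never an AE record. No number for Day 1 findings is therefore justified.

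**Conclusion.** The point holds in a limited form. Protocol 7.1.5 and footnote 3 of Tables 17 to 20 contradict the MAAE definition in the glossary, protocol 7.4.4 and SAP 6.3.1. For a new finding at a scheduled post-dose visit, nothing in the SAP removes the wrong label. The result is a risk of over-counting and of inconsistent classification between sites, of unknown size and possibly zero. It rests on two conditions: that some sites follow 7.1.5 as written, and that such findings occur without an unscheduled visit.

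Two stronger readings go too far. One is that the endpoint is over-counted as a matter of fact. The text is a recommendation to sites, and the documents do not show how sites applied it. The other is that COVID-19 materially distorts the MAAE count. Protocol 7.1.6 requires symptoms plus a positive RT-PCR for a case and arranges an illness visit when symptoms qualify. Protocol 7.4.4 names COVID-19 among its examples of unscheduled assessments. Most cases therefore meet the definition, and SAP 6.5 summarises infections separately. What remains on COVID-19 is a difference in wording between 7.4.4 and 7.1.6 with 3.1.

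**What to change.** 1. **Protocol 7.1.5 and footnote 3 of Tables 17 to 20.** Reconcile with 7.4.4. A clinically significant post-dose finding is recorded as an AE at any visit, including after Day 28, and is flagged as an MAAE only if it led to an unscheduled healthcare visit. The provision for findings after Day 28 must be explicit, so that narrowing the MAAE label does not drop non-serious findings from collection.
2. **SAP 6.3.1.** State that the medically-attended flag is derived from the unscheduled visit. The documents do not show whether the AE page of the eCRF records visits to outside providers. If it does not, the query below has to supply that information.
3. **Data query before database lock.** Review MAAEs first identified at scheduled visits and confirm whether an unscheduled visit followed.
4. **Protocol 7.4.4.** Align its sentence on confirmed COVID-19 cases with the confirmed-symptomatic wording in 7.1.6 and 3.1.

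The protocol is dated October 2023 and estimates last participant completion for December 2023. The SAP rule and the query will therefore do most of the work, and the protocol wording mainly clears the record. The cost is a wording clarification, one short query and slightly lower MAAE counts.
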